15.3.2 Secondary Biological Objectives

We will estimate within-patient changes in immune response (ELISPOT, cytokines array, flow cytometric analysis and NK cell activity) from baseline to vaccine #3 and compare these changes between treatment and control groups using the Wilcoxon rank sum test. To assess the effect of these changes in immune response on OS and PFS subsequent to vaccine #3, we will conduct a landmark analysis within the framework of Cox proportional hazards models of post-baseline OS and PFS. These models will incorporate Indicators for treatment arm, change in immune response parameters from baseline to vaccine #3, interaction between treatment arm and immune response changes, and potential confounders.

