Chemotherapeutic agents frequently used in cancer therapy, however, often induce a profound lymphopenia that may inhibit even the most potent anti-tumor immune responses. TMZ, a methylating chemotherapeutic agent, has recently shown efficacy in some patients with newly diagnosed GBM(Stupp, Mason et al. 2005) and is now routinely given to these patients during and after RT. Therapeutic TMZ, however, also induces a profound lymphopenia.

Human CMV antigens have been shown by a number of laboratories to be expressed in a high proportion (>90%) of malignant gliomas. We have recently completed a phase I/II clinical trial exploring the safety, immunogenicity, and potential clinical efficacy of autologous pp65 RNA-pulsed DC vaccines in patients with newly-diagnosed GBM. This trial explored the capacity to enhance DC migration to VDLNs using inflammatory skin preparations administered prior to pp65 RNA-loaded DC vaccines in a randomized pilot trial design (n=12 patients). The results of these studies demonstrated the capacity to safely expand CMV-specific cellular and humoral immunity in patients with GBM using autologous pp65 RNA-pulsed DC vaccines and demonstrated a strong correlation with successful DC migration to VDLNs and clinical outcomes ($R=0.73$, $P=0.007$; *Pearson correlation coefficient*). Strikingly, patients randomized to receive a tetanus toxoid booster as an inflammatory stimulus at the vaccine-site showed an increased migration of DCs to VDLNs ($P=0.04$) and a corresponding increased progression-free and overall survival ($P=0.01$ *Logrank analysis*). These results suggested that successful DC trafficking *in vivo* is associated

with improved outcomes in patients with GBM receiving pp65 RNA-pulsed DC vaccines and that inflammatory stimuli that enhance DC migration improve the efficacy of this treatment modality. In support of this hypothesis, we found increased levels of chemokines that facilitate DC migration in patients randomized to the tetanus group. Additionally, we have corroborated these findings using a transgenic mouse model employing GFP+ mice to evaluate DC migration. Pp65 RNA-pulsed DCs are a novel and promising therapeutic modality for patients with GBM, and our studies indicate that DC migration to VDLNs constitutes a major biological axis for potential clinical intervention in order to enhance the efficacy of this treatment strategy.

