9.6 Removal of PBMCs by Leukapheresis

Prior to the initiation of TMZ and external beam RT and again 2 to 4 weeks after vaccine #3, subjects will undergo leukapheresis in accordance with **SOP-UFBTIP-131**. Intravenous access will be obtained by placing two large gauge catheters into the antecubital veins bilaterally or by using a dialysis-type central venous catheter that will allow for large volume apheresis. In addition to research protocol consent, additional surgical/procedural consent will be obtained for placement of the central venous catheter by the surgeon/proceduralist. Placement of this special catheter may require use of fluoroscopy. The procedure will be conducted using the COBE® Spectra™ Apheresis System (or equivalent). A sample of each leukapheresis product will be used for immunologic monitoring.

Subjects may undergo additional leukapheresis, if needed, to generate up to 10 DC vaccines. Additional leukapheresis procedures may be performed at anytime at the discretion of the PI to

limit treatment interruption/delay as much as possible. When feasible, additional leukapheresis should be scheduled no earlier than 1 week following DC vaccination and prior to the following TMZ cycle. After the leukapheresis, TMZ cycle may occur as scheduled.

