9.7 Tetanus and Diphtheria Toxoid Booster and site pre-treatment

At time of first vaccination, all patients, regardless of tetanus vaccination history, will receive a Td booster (5 Lf) intramuscularly into the deltoid muscle.

Subjects will undergo vaccine site pretreatment with a one-fifth dose of Td (1 Lf) (treatment arms 1 and 2) or saline (arm 3) intradermally 6-24 hours prior to Vaccine #3, #6, and #9, alternating site for each pretreatment

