12 IMMUNOLOGICAL RESPONSE EVALUATIONS

Immunological response evaluations for baseline values will be conducted on PBMCs collected at the time of the initial leukapheresis sample. Immunologic response evaluations will also be performed from peripheral blood obtained prior to select vaccinations. The primary comparison for immunologic endpoints will be baseline response (pre-leukapheresis or P1) compared to response post vaccine #3 (post-leukapheresis or P2). Our previous studies demonstrated a significant increase in immunologic responses in vaccinated patients that peaked after the third vaccine in most subjects. A comparison of pre-therapy lymphocyte function to additional vaccine time points may be conducted on an exploratory basis. Arms 1 and 2 (pp65-shLAMP RNA-pulsed DCs and pp65-fLAMP RNA-pulsed DCs) will be analyzed separately for immunologic endpoint comparisons. Studies examining DNA vaccines using full-length LAMP1 fusion antigens compared to truncated versions of the LAMP protein have demonstrated that increased antigen expression, secretion of LAMP fusion proteins, enhanced antibody titers, increased cytokine release by CD4+ and CD8+ T cells, improved central memory T cell differentiation, and enhanced

polyfunctional T cell responses, all were dependent on full-length LAMP1 fusion antigens(Godinho, Matassoli et al. 2014). Truncated LAMP fusions that did not contain the luminal domain of LAMP were much less efficient in this wide spectrum of immunologic analyses. As a primary biologic analysis and secondary endpoint of this study, we will compare the immunologic responses in patients vaccinated with CMV pp65-fLAMP RNA-pulsed DCs (Arm 1) to patients vaccinated with CMV pp65-shLAMP RNA-pulsed DCs (Arm 2) across this spectrum of responses.

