The laboratory of UFBTIP will conduct a flow cytometric analysis that aims to quickly detect the activation of T cells through CD69 and exhaustion via PD-1. A 13-color assay will be used to monitor the polyfunctional immune response of patients' CD4 and CD8 cells. The analysis will also include an examination of the phenotypic distribution of T cells that respond to the assay, including naive, effector, central memory, effector memory, and terminal effector cells. Additionally, the same panel will be used to analyze regulatory T cells (identified as CD3+CD4+CD25+FoxP3+), natural killer cells (CD56+), natural killer T cells (CD56+CD3+), invariant natural killer T cells (CD56+CD3+TCR-va24+), and cell viability (measured through the Live/Dead Fixable Blue Viability Assay) (as seen in Figure 13).

Immediately preceding select vaccinations peripheral blood will be drawn into vacutainer tubes containing ACD. PBMC will be separated by density gradient centrifugation on ficoll-Hyopaque and then cryopreserved until the day of immune monitoring operation..

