12.3 Multiplex Cytokine Quantification

The UFBTIP laboratory will perform a Multiplex cytokine analysis to detect multiple cytokines secreted by lymphocytes. This analysis will use a multiplex kit on the Meso Scale Discovery platform to simultaneously examine Type 0,1,2, and 3 cytokines (IFN- γ , IL-1 β , IL-2, IL-4, IL-6, IL-8, IL-10, IL12p70, IL-13, and TNF- α) secreted by T cells. Prior to select vaccinations, peripheral blood will be drawn into vacutainer tubes containing silicone and micronized silica particales (SST) to isolate patient serum. This serum will be cryopreserved until the day of the Multiplex cytokine assay.

12.1 Single Cell Gene Expression and Immune Profiling For Monitoring Changes in Glioblastoma Patients with Sustained Radiographic Response to CMV pp64-LAMP RNA-Pulsed Dendritic Cell-Based Vaccines.

The application of single cell sequencing as a novel immune monitoring platform can be used to identify the molecular mechanisms of immune response to dendritic cell- based vaccines, trace the cell types and states involved, and uncover novel biomarkers for immunotherapy. We will perform

single-cell RNA Seq analysis of longitudinal peripheral blood mononuclear cells (PBMCs) in selected patients.

Cell preparation: Frozen cell vials with PBMCs collected at different time points following DC vaccination of selected ATTAC patients will rapidly be thawed in a 37°C water bath. Thawed PBMCs will be washed and filtered with a cell drainer. Cells will be collected by centrifugation and subsequently counted with hemocytometer. For Single cell RNA-seq, single cell suspension will be loaded onto Chromium Controller according to the manufacturer's specifications and TCR-seq libraries will be prepared via PCR amplification with primers specific to the TCR and for 5' gene expression library construction. Pre-processing of scRNA-seq data will be performed using specific software for identification of cell types.

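### Section 15.3.2 ends the immune change at vaccine #3 and Section 12 ends it at P2; read literally, 15.3.2 can pick a sample taken hours after Td in Arms 1 and 2 but after saline in Arm 3

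*Combined protocol and SAP*

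**What the plan says.** Section 15.3.2 defines the change score: "We will estimate within-patient changes in immune response (ELISPOT, cytokines array, flow cytometric analysis and NK cell activity) from baseline to vaccine #3". A Wilcoxon rank sum test sets the vaccine arms against control. The section then relates that change to later OS and PFS in landmark Cox models with terms for arm, immune change, their interaction and confounders. Survival there is counted after vaccine #3. No blood sample is named.

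Section 12 does name one: "The primary comparison for immunologic endpoints will be baseline response (pre-leukapheresis or P1) compared to response post vaccine #3 (post-leukapheresis or P2". Section 9.6 dates P2: "again 2 to 4 weeks after vaccine #3, subjects will undergo leukapheresis".

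The skin preparation differs by arm. Section 9.7 says: "Subjects will undergo vaccine site pretreatment with a one-fifth dose of Td (1 Lf) (treatment arms 1 and 2) or saline (arm 3) intradermally". This is done 6-24 hours before vaccines #3, #6 and #9. Section 10.4 and footnote 14 to Section 10.7 schedule blood at both leukaphereses, before vaccines 1, 2, 3, 4, 7 and 10, at the imaging time points (University of Florida site only) and at progression. For flow cytometry, Section 12.2 says: "Immediately preceding select vaccinations peripheral blood will be drawn into vacutainer tubes containing ACD". For serum, Section 12.3 says: "Prior to select vaccinations, peripheral blood will be drawn into vacutainer tubes containing silicone". Neither says which vaccinations are meant.

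**The concern.** Two sections give different end points for the same change score, and an analyst could follow either. The one suggested by 15.3.2 lies next to an intervention that differs between the groups being compared. If the sample is drawn at the vaccine #3 visit, Arms 1 and 2 have had an intradermal toxoid challenge within the previous day and Arm 3 has had saline. A treatment-control difference in serum cytokines could then reflect the skin preparation rather than the pulsed DCs. All patients also receive a Td booster at vaccine #1 (Section 9.7), so every arm is recently boosted, but only Arms 1 and 2 are challenged again before vaccine #3.

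The protocol's own background makes a Td-related change in soluble factors plausible. On the earlier trial, Section 4 reports: "we found increased levels of chemokines that facilitate DC migration in patients randomized to the tetanus group". It gives no sampling time and no size.

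**Working it through.** The plan states no figure for this analysis, so there is none to reproduce. The check sets the schedule out and then sizes the problem under stated assumptions.

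**1. Which draws follow a skin preparation?** Skin preparation precedes vaccines {3, 6, 9} (Section 9.7). Pre-vaccine blood is drawn before vaccines {1, 2, 3, 4, 7, 10} (Section 10.4). The only common element is vaccine #3.

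**2. Time from skin preparation to each candidate sample.**
- Draw at the vaccine #3 visit: 6 to 24 hours, after two vaccines.
- P2: from 14 days + 6 hours = 14.25 days to 28 days + 24 hours = 29 days, after three vaccines. Section 12 reports that responses in earlier studies mostly peaked after the third vaccine.

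**3. Which sample does 15.3.2 mean?** Pointing to the pre-vaccine draw: a landmark covariate must be known at the landmark, and a P2 value is not known at vaccine #3; Section 12.3 mentions only serum drawn before vaccinations. Pointing to P2: Section 12 names it explicitly as primary. The text does not settle the matter.

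**4. Illustrative size.** Assumptions: 80 against 40 patients (Section 15.2), normal change scores with SD 1, no DC effect, a Td-only shift *d* in Arms 1 and 2, and a Wilcoxon rank sum test at two-sided 0.05 (15.3.2 sets no level). Simulation with 10,000 runs:

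| *d* (SD) | Rejections |
|---|---|
| 0 | 4.9% |
| 0.2 | 16.9% |
| 0.5 | 69.9% |
| 0.8 | 97.9% |

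Closed-form check: the expected z is about d × √(80 × 40/120) × √(3/π) = d × 5.164 × 0.977 = 5.046d. For d = 0.2, z = 1.01 and the rejection rate is about Φ(1.01 − 1.96) = 0.17. For d = 0.5, z = 2.52 and it is about Φ(2.52 − 1.96) = 0.71. With 80% of patients contributing (64 against 32; 3,000 runs), the simulated rates are 13.9% and 59.7%.

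**5. Effect on the landmark Cox models.** Let A = 1 in a vaccine arm and 0 in control, X be the immune change without Td, and X′ = X + cA the observed change, with c constant. Since A² = A, the linear predictor b₁A + b₂X + b₃AX equals (b₁ − c·b₂ − c·b₃)A + b₂X′ + b₃AX′. The slopes b₂ and b₃ are unchanged; only the arm coefficient moves. A Td reaction that varies between patients would not cancel in this way; it is not quantified here.

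**The case against.** A reader might infer that the plan definitely analyses blood drawn just after Td, and so measures the Td reaction instead of the vaccine response. The documents do not support that.

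- Section 15.3.2 names no sample, and the one section that does names P2.
- Nothing fixes the order of the routine draw before vaccine #3 and the skin preparation. The wording that puts the draw immediately before vaccination occurs in the flow cytometry section, for unspecified vaccinations; the serum section says only that blood is taken beforehand. At the University of Florida a separate imaging-related sample precedes pretreatment (Section 9.9).
- ELISPOT, called the primary cellular assay, uses CMV peptides and subtracts the no-peptide background (Section 12.1), so a non-specific reaction should affect it less.
- Td belongs to the regimen in the primary objective (Section 5.2.1). A Td contribution is not a false positive for a regimen-against-control question.
- Full-length against short LAMP, which Section 12 treats as the primary biologic analysis, compares two arms that both receive Td.
- A constant Td shift leaves the within-arm slopes of the landmark models intact (step 5).
- The chemokine remark in Section 4 does not show an acute rise in the cytokines listed in Section 12.3, and the shift sizes in step 4 are assumptions.

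All of this stands and narrows the point. It does not remove the mismatch between Sections 12 and 15.3.2, nor the fact that the landmark wording in 15.3.2 fits the sample before vaccine #3 better than P2.

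**Conclusion.** The point holds as a conflict between two sections with a real consequence under one reading. Section 12 ends the change at P2; 15.3.2, read literally, ends it at a draw that follows two vaccines. If that draw is taken at the vaccine visit, it comes 6-24 hours after Td in Arms 1 and 2 and after saline in Arm 3. The treatment-control contrast is then confounded with an acute Td reaction, most plausibly for unstimulated serum cytokines and for activation markers such as CD69 in the flow panel.

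The size is unknown. The 17% to 70% range depends on assumed shifts of 0.2 to 0.5 SD, 80 against 40 patients with samples, and a two-sided 0.05 test. Under this reading, what is lost is attribution of the difference to the pulsed DCs. The primary OS comparison is untouched.

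**What to change.** In Section 15.3.2, replace vaccine #3 as the end of the change with the P2 sample, matching Section 12, for both the Wilcoxon comparison and the immune-survival models. Set the OS and PFS landmark at the P2 date, so that the covariate is known when follow-up starts. Reserve any vaccine #3 sample drawn after skin preparation for exploratory use, such as the chemokine objective in Section 5.2.3, and record its time relative to the skin preparation.

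No new sampling is needed: footnote 14 to Section 10.7 already schedules ACD-A and SST tubes at the second leukapheresis. The cost is in numbers and scope. Patients without a P2 sample, or who die or progress before P2, leave these analyses, and the survival models then describe only patients who reach P2. The University of Florida draw before pretreatment cannot replace P2, because it exists at that site only.

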16 REGULATORY REQUIREMENTS AND ETHICAL CONSIDERATIONS

The study will be conducted in accordance with the protocol, FDA Regulations 21 CFR parts 50, 54, 56 and 312, HHS Regulations 45 CFR part 46, the International Conference on Harmonization guidelines for Good Clinical Practice (ICH E6), and applicable institutional, local and state requirements. All personnel involved in the conduct of this study have completed human subjects protection training in accordance with local institutional requirements.

16.1 Institutional Review Board

Each site will obtain Institutional Review Board (IRB) approval of the protocol and protocol related documents including consent forms, prior to initiating the study. The study may be initiated only after the Principal Investigator has received written and dated approval from the IRB and notification of activation from the Coordinating Center. Amendments to the protocol must originate with the Protocol Chair and be approved by the IRB prior to implementation. The FDA will be notified as required under 21 CFR 312.30.

The Principal Investigator must submit and obtain approval from the IRB for all subsequent protocol amendments and changes to the informed consent form in accordance with 21 CFR 56 and local policy prior to implementation except where necessary to eliminate apparent immediate hazard to the subject. If a change is made to eliminate an apparent immediate hazard, the PI must notify the IRB in accordance with local policy, the Protocol Chair and the sponsor within 24 hours. The IND sponsor will notify the FDA of such change in accordance with 21 CFR 312.30. Each investigator will follow the requirements of their local IRB for periodic reporting of study progress, reporting of serious adverse events, unanticipated problems, and protocol deviations or violations, safety monitoring reports and study completion. Protocol exceptions must have approval from the Protocol Chair, FDA (as applicable through the sponsor) and IRB prior to implementation.

The Principal Investigator must obtain protocol re-approval as required by the IRB, but not less than once per year.

16.2 Informed Consent

Informed consent will be obtained and documented in accordance with 21 CFR 50 and the requirements of the IRB. The informed consent form must be written in a manner that is understandable to the subject population. Prior to its use, the informed consent form must be approved by the IRB. For potential subjects whose primary language is not English, investigators should follow the requirements and determinations of the reviewing IRB and any applicable institutional procedures.

The Principal Investigator or authorized key personnel will discuss with the potential subject the purpose of the research, methods, potential risks and benefits, subject concerns, and other study-related matters. This discussion will occur in a location that ensures subject privacy and in a manner that minimizes the possibility of coercion. Appropriate accommodations will be made available for potential subjects who cannot read or understand English or are visually impaired. Potential subjects will have the opportunity to contact the Principal investigator or authorized key personnel with questions, and will be given as much time as needed to make an informed decision about participation in the study.

Before conducting any study-specific procedures, the Principal Investigator must obtain written informed consent from the subject or a legally authorized representative. The original informed consent form will be maintained with the subject's study records, and a copy of the informed consent form will be provided to the subject. The Principal Investigator is responsible for asking the subject whether the subject wishes to notify his/her primary care physician about participation in the study. If the subject agrees to such notification, the Principal Investigator will inform the subject's primary care physician about the subject's participation in the clinical study.

16.3 Privacy, Confidentiality, and Data Storage

The Principal Investigator will ensure that subject privacy and confidentiality of the subject's data will be maintained. To protect privacy, every reasonable effort will be made to prevent undue access to subjects during the course of the study. Prospective participants will be consented in an exam room where it is just the research staff, the patient and his family, if desired. For all future visits, interactions with research staff (study doctor and study coordinators) regarding research activities will take place in a private exam room. All research related interactions with the participant will be conducted by qualified research staff who are directly involved in the conduct of the research study.

To protect confidentiality, subject files in paper format will be stored in secure cabinets under lock and key accessible only by the research staff. After agreeing to participate, some patient identifiers will be collected, used and/or recorded, including, but not limited to name, date of birth, telephone number, address, dates from health records and a unique patient number. This information may be kept in patient binders as well as recorded in the respective eCRF. Images collected will be as de-identified as possible. Only approved study personnel and those included in the HIPAA Authorization will have access to identified, partially identified, and/or coded data. Data and specimens will be collected, stored and transported with consideration for subject privacy and confidentiality. Electronic records of subject data will be maintained in a password-protected computer. Access to electronic databases will be limited to the Principal Investigator and key study personnel. Data stored on portable memory devices will be de-identified.

Upon completion of the study, research records will be archived and handled per local policy.

Subject names or identifiers will not be used in reports, presentations at scientific meetings, or publications in scientific journals.

